2.1.3 Secondary endpoint

Pharmacokinetic endpoint

The following secondary endpoint will be determined for ethinylestradiol and levonorgestrel based on the sampling times given in the Flow Chart:

- AUC_{0-∞} (area under the concentration-time curve of the analyte in plasma over the time interval from 0 extrapolated to infinity)

3. DESCRIPTION OF DESIGN AND TRIAL POPULATION

3.1 OVERALL TRIAL DESIGN AND PLAN

The trial will be performed according to an open-label, two-period, fixed sequence design. Female patients, who are considered eligible for therapy with nintedanib to treat their systemic sclerosis associated interstitial lung disease (SSc-ILD), have given their informed consent, and meet all inclusion criteria and none of the exclusion criteria, will receive the first dose of Microgynon[®] at the latest 3 days before the first administration of nintedanib. A second dose of Microgynon[®] will be administered at Visit 6, after continuous nintedanib intake for at least 10 consecutive days. Visit 6 may take place between Day 11 and Day 25 of nintedanib administration, depending on the visit scheduling and/or the patient's condition. However, if a temporary interruption or nintedanib dose reduction has to take place (see Section 4.2.1), additional bottles of nintedanib may have to be dispensed at Visit 6 (or at an Unscheduled Visit) and the Visit 5 - Visit 6 visit window may have to be extended accordingly.

Blood for PK evaluation will be collected on the days of Microgynon[®] administration, and on the following 2 days. Adverse events and concomitant therapies will be recorded throughout the trial period, which ends once the patient has performed the End of Study (EOS) Visit. An overview of all relevant trial activities is provided in the [Flow Chart](#). For visit schedule and details of trial procedures at selected visits, refer to Section 6.

[figure not shown]

Figure 3.1: 1 Visit schedule

3.2 DISCUSSION OF TRIAL DESIGN, INCLUDING THE CHOICE OF CONTROL GROUP(S)

Female patients with SSc-ILD will be included in this trial, if they are considered eligible for this trial, i.e. if they meet the inclusion and none of the exclusion criteria. Patients will be asked before starting the nintedanib therapy whether they would agree to participate in this Phase I trial. The patients will not have any benefit from intake of Microgynon[®] on two days during the trial period. The patients will be supervised by their treating physicians and adverse events occurring during the trial phase will be reported. The patients who complete this trial will be given the opportunity to continue nintedanib treatment in the roll-on Trial 1199-0225.

For this trial a non-randomised design was selected because the interaction with Microgynon[®] will be investigated in patients with a clearly defined treatment schedule of nintedanib. Therefore, kinetics of Microgynon[®] alone can only be determined before the start of nintedanib treatment. Systematic errors resulting from the fixed sequence are expected to be low because the trial duration is short enough so that nonspecific time-effects will be less important.

In the fixed sequence design, each patient serves as her own control. The comparison between treatments is based on a comparison within patients rather than between patients. This trial design, therefore, removes inter-patient variability from the comparison between treatments ([R94-1529](#)).

As requested per EMA Guideline ([P15-06991](#)), this trial will be performed to exclude potential inductive effects of nintedanib on the kinetics of Microgynon[®]. Induction of CYP3A4, the major enzyme involved in biotransformation of ethinylestradiol and levonorgestrel, is mediated by the nuclear receptor Pregnane X Receptor (PXR). Referring to the well characterized PXR inducer rifampicin, a full induction of drug metabolizing enzymes is reached in about one week after start of rifampicin treatment ([P03-08008](#)). Potential inductive effects of nintedanib will be investigated after 10 consecutive dosing days with nintedanib.

The open-label treatment is not expected to bias the results, since the study endpoints are derived from measurement of plasma concentrations of the analytes.

3.3 SELECTION OF TRIAL POPULATION

A total of 14 patients, who completed the trial and can be analysed for both treatment periods, are needed for the purpose of the trial. It is assumed that up to approximately 24 patients may have to be enrolled by approximately 12 sites to achieve the goal that 14 patients completed the trial and have data evaluable for the PK analysis.

Sites will be experienced in the management of patient with SSc-ILD and are each expected to include approximately 2 patients. Additional sites may be initiated and 'non-productive' sites may be closed to ensure sponsor's timelines

Screening of patients for this trial is competitive, i.e. screening for the trial will stop at all sites at the same time once a sufficient number of patients has been screened. Investigators will be notified about screening completion and will then not be allowed to screen additional patients for this trial.

To be able to assess the drug-drug interaction of nintedanib with contraception in female patients as accurately as possible, certain restrictions apply: please refer to Section [4.2.2.1](#). A log of all patients enrolled into the trial (i.e. who have signed informed consent) will be maintained in the Investigator Site File (ISF) irrespective of whether they have been treated with investigational drug or not.

If a patient is enrolled in error (does not meet all inclusion criteria or meets one or more exclusion criteria on the day of enrolment), the sponsor should be contacted immediately.

Re-screening of a previously declared 'screen failed' patient is allowed, but only if the previous reason(s) for screen failure (e.g. an exclusion criterion) is resolved in the time between the previous screening and the re-screening. The re-screened patient must sign a new informed consent and will get a new unique patient number.

3.3.1 Main diagnosis for trial entry

Outpatients diagnosed with Systemic Sclerosis associated Interstitial Lung Disease (SSc-ILD), based upon classification according to the American College for Rheumatologists / European League against Rheumatism (ACR / EULAR) 2013 criteria ([R14-5055](#)) and a chest high resolution computer tomography (HRCT) demonstrating fibrotic/interstitial changes, are eligible for inclusion if they fulfil all the inclusion criteria (Section [3.3.2](#)) and do not present any of the exclusion criteria (Section [3.3.3](#)).

Please refer to Section [8.3.1](#) (Source Documents) for the documentation requirements pertaining to the in- and exclusion criteria.

3.3.2 Inclusion criteria

1. Signed and dated written informed consent in accordance with ICH-GCP and local legislation prior to admission to the trial.
2. Female patients \geq 18 years at Screening Visit 1.
3. A woman of non-child bearing potential, i.e. being postmenopausal¹ or permanently sterilised (e.g. hysterectomy, bilateral oophorectomy, or bilateral salpingectomy), or a woman of childbearing potential correctly and consistently using a highly effective method of non-hormonal birth control (i.e. IUD or bilateral tubal ligation) together with barrier methods² at least 30 days prior to first administration of Microgynon[®] (Visit 2), during the trial and for 3 months after last intake of nintedanib. See also Section [4.2.2.4](#).

A list of contraception methods fulfilling these criteria is provided in the patient information.

(Note: ¹A postmenopausal state is defined as no menses for 12 months without an alternative medical cause. A high follicle stimulating hormone (FSH) level in the postmenopausal range may be used to confirm a post-menopausal state in women not using hormonal replacement therapy; in questionable cases a blood sample with simultaneous levels of FSH above 40 U/L and estradiol below 30 ng/L is confirmatory [R16-0373]). ² Possible barrier methods: male or female condom, or diaphragm or cervical cap, to be used in combination with spermicide.) For further details, see Section [4.2.2.4](#).

4. Patient with Systemic Sclerosis associated Interstitial Lung Disease (SSc), fulfilling the 2013 ACR / EULAR classification criteria for SSc.
5. ~~SSc disease onset (defined by first non-Raynaud symptom) must be within 7 years of Visit 1.~~ (No longer applicable with global protocol amendment 2)
6. SSc related Interstitial Lung Disease pattern must be confirmed by HRCT performed within 12 months of Visit 1³. The extent of fibrotic disease in the lung must be $\geq 10\%$ on HRCT, assessed by local review.

(Note : ³ If the patient does not have a HRCT within 12 months of Visit 1, but meets all the other inclusion and no exclusion criteria, the HRCT scan can be performed for the purpose of participation in the trial, if accepted by local regulations (except for patients in Germany, as was also decided for the phase III SENSICIS trial 1199.214)

7. FVC $\geq 40\%$ of predicted normal at Visit 1 (refer to Appendix [10.1](#)).
8. DLCO (corrected for Hb [Visit 1]): 30 % to 89% of predicted at Visit 1 (refer to Appendix 10.1).

3.3.3 Exclusion criteria

1. AST, ALT $> 1.5 \times$ ULN.*
2. Bilirubin $> 1.5 \times$ ULN.*
3. Creatinine clearance < 30 mL/min* calculated by Cockcroft–Gault formula ([10.2](#)).

(Note:* Laboratory parameters from Visit 1 have to satisfy the laboratory threshold values as shown above. In case at Visit 2 the results do no longer satisfy the entry criteria, the Investigator has to decide whether it is justified that the patient remains in the trial. The justification for decision needs to be documented. Laboratory parameters that are found to be abnormal at Visit 1 are allowed to be re-tested (once) if it is thought to be a measurement error (i.e. there was no abnormal result of this test in the recent history of the patient and there is no related clinical sign) or the result of a temporary and reversible medical condition, once that condition is resolved).

4. Clinically relevant anaemia at investigators discretion.
5. Airway obstruction (pre-bronchodilator FEV₁/FVC < 0.7) at Visit 1, or other clinically significant pulmonary abnormalities in the opinion of the investigator.

6. Significant Pulmonary Hypertension (PH) defined by any of the following:
 - Previous clinical or echocardiographic evidence of significant right heart failure
 - History of right heart catheterisation showing a cardiac index ≤ 2 l/min/m²
 - PH requiring therapy with prostacyclines (parenteral or oral, e.g. epoprostenol, treprostinil, selexipag)
7. Cardiovascular diseases, any of the following:
 - Severe hypertension, uncontrolled under treatment ($\geq 160/100$ mmHg), within 6 months of Visit 1
 - Myocardial infarction within 6 months of Visit 1
 - Unstable cardiac angina within 6 months of Visit 1
8. More than 3 digital fingertip ulcers at Visit 1 or a history of severe digital necrosis requiring hospitalization or severe other ulcers at discretion of the investigator.
9. Bleeding risk, any of the following:
 - a. Known genetic predisposition to bleeding, according to the judgement of the investigator.
 - b. Patients who require (also during the trial):
 - i. Fibrinolysis, full-dose therapeutic anticoagulation (e.g. vitamin K antagonists, direct thrombin inhibitors, heparin, hirudin)
 - ii. High dose antiplatelet therapy
[Note: Prophylactic low dose heparin or heparin flush as needed for maintenance of an indwelling intravenous device (e.g. enoxaparin 4000 IU s.c. per day), as well as prophylactic use of antiplatelet therapy (e.g. acetyl salicylic acid up to 325 mg/day, or clopidogrel at 75 mg/day, or equivalent doses of other antiplatelet therapy) are not prohibited].
 - c. History of hemorrhagic central nervous system (CNS) event within 12 months of Visit 1.
 - d. Any of the following within 3 months of Visit 1:
 - i. Haemoptysis or haematuria
 - ii. Active gastro-intestinal bleeding or GI – ulcers
 - iii. Gastric antral vascular ectasia (GAVE)
 - iv. Major injury or surgery (investigators judgement)
 - e. Coagulation parameters: International normalised ratio (INR) >2 , prolongation of prothrombin time (PT) and partial thromboplastin time (PTT) by >1.5 x ULN at Visit 1.
10. History of major thrombo-embolic event (e.g. stroke/transient ischemic attack, deep vein thrombosis, pulmonary embolism) within 12 months of Visit 1.

11. Previous hematopoietic stem cell transplantation (HSCT), or HSCT planned within the next year.
12. Major surgical procedures planned to occur during trial period.
13. Other disease or conditions that may interfere with testing procedures (e.g. inability to tolerate interruption of supplemental oxygen for pulmonary function testing) or in the judgment of the Investigator may interfere with trial participation or may put the patient at risk when participating in this trial (e.g. severe GI symptoms due to SSc, clinically relevant intestinal pseudoobstruction).
14. Gastrointestinal disorders or abnormalities that would interfere with absorption of the trial drugs, including patients with clinical signs of malabsorption or needing parenteral nutrition.
15. Patients with underlying chronic liver disease (Child Pugh A, B, C hepatic impairment).
16. Patients with a history of Scleroderma Renal Crisis.
17. Life expectancy of <2.5 years for disease other than SSc in investigator assessment.
18. Patients who must or wish to continue the intake of restricted medications, e.g. P-glycoprotein (P-gp), cytochrome P450 3A4 (CYP3A4) inhibitors or inducers medications, certain immunosuppressive agents, or any other drug considered likely to influence the motility or absorbance of the trial medication in the gastrointestinal tract, or interfere with the safe conduct of the trial. (see Section [4.2.2.1](#) for a complete list and further details).
19. Known hypersensitivity to the trial medication or its components (i.e. soya lecithin).
20. Any contraindication to nintedanib, ethinylestradiol or levonorgestrel (Microgynon[®]), as specified in the respective labels.
21. Previous treatment with nintedanib or pirfenidone.
22. Previous enrolment in this trial or previous participation in the SENSICIS[®] trial (1199.214) or the roll-over trial 1199.225.
23. Currently enrolled in another investigational device or drug trial, or less than 30 days since ending another investigational device or drug trial(s), or receiving other investigational treatment(s).
24. Patients not expected to comply with the protocol requirements, not able to understand or follow trial procedures, including completion of the self-administered questionnaires, or not expected to complete the trial as scheduled.
25. Chronic alcohol or drug abuse or any condition that, in the investigator's opinion, makes the patient an unreliable trial participant or unlikely to complete the trial.
26. Women who are pregnant, nursing, or who plan to become pregnant while in the trial.

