- ⁵ Echocardiography will at least be performed in patients with a history of pulmonary hypertension at Screening (time window: Visit 1 to Visit 2).
- ⁶ Self-reported outcome questionnaires must always be done by the patients in a quiet place prior to any other visit procedure. Order of questionnaires: 1. SGRQ, 2. SHAQ, 3. SCTC GIT, 4. Patient's global VAS (see Appendix [10.3](#)). The SCTC GIT will only be done in countries if the locally required language version is available.
- ⁷ Laboratory safety test at Visit 5, Day 1 should be done prior to intake of nintedanib in order to get baseline laboratory values without Microgynon[®] (past the Microgynon[®] residual effect period (REP) of 3 days) or nintedanib related effects.
- ⁸ PK sampling before intake of nintedanib in Period 2 (Visits 6-8) will be done as described in the PK overview on the following pages, which also contains detailed information about other assessments and timing of intake of meals and water.
- ⁹ In Period 2/Visit 6 Nintedanib will be administered first directly followed by Microgynon[®] and both have to be intaken within 1 minute on the PK day.

- ¹⁰ Detailed information about timing and assessments during PK days in Periods 1 and 2 can be found in the overviews on the following pages. PK sampling after Microgynon[®] intake will be done at approximate timepoints t = +30 min to +12 h (9 times), at t = +24 h and t = +48 h. During PK day in Periods 1 and 2, at t = 20 h and 4 h, administration of 240 mL of water.
- ¹¹ Pregnancy testing will only be done in women of childbearing potential: β -HCG will be performed at Visit 1 only. Urine dipstick pregnancy tests will be performed at Visits 5 and EOT and FU visit if applicable. If urine test is not acceptable to local authorities, a blood test can be also done by local laboratory if needed.

Detailed overview and order of assessments on PK days in Period 1:

Period 1, Visits 2-4				
Day	Relative. time to Microgynon® intake [h:min]	Approx. Clock Time* [h:min]	Assessment/comment	PK blood for EE and LE
Visit 2, Day -3	Pre-dose		Physical examination	
	Pre-dose		Review in/exclusion criteria	
	Pre-dose		Vital signs	
	Pre-dose		12-lead ECG	
	Pre-dose		Safety Laboratory tests (preferably after ECG)	
	Pre-dose		Adverse events	
	Pre-dose		Concomitant therapy	
	Pre-dose		Compliance check	
	-00:35	07:25		x
	-00:30	07:30	Breakfast (standardized)**	
	00:00	08:00	Microgynon® intake*	
	00:30	08:30		x
	01:00	09:00		x
	01:30	09:30		x

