in two replicate Phase III (INPULSIS 1 and 2) trials. These were randomised, double-blind, placebo-controlled trials comparing treatment with nintedanib twice daily to placebo for 52 weeks. A statistically significant reduction in the annual rate of decline of FVC (in mL) was demonstrated in patients receiving nintedanib 150 mg b.i.d. compared to patients receiving placebo. The treatment effect of nintedanib compared to placebo on FVC was consistent in all 3 studies, i.e. a relative reduction of decline of approximately 50%. Supporting the effect of nintedanib on slowing disease progression ([P14-07514](#); [P11-11216](#)), nintedanib 150 mg b.i.d. significantly reduced the risk of first acute exacerbation compared with placebo in INPULSIS-2 and in the TOMORROW trial and reduced the risk of acute exacerbations (adjudicated) by 68% in a pre-specified sensitivity analysis of pooled data from the INPULSIS trials.

The safety profile of nintedanib has been investigated comprehensively. The proportion of patients with serious adverse events was similar in the nintedanib and placebo groups.

The risks of treatment with nintedanib in adult patients are primarily related to the gastrointestinal tract (diarrhoea, nausea, vomiting, abdominal pain, and pancreatitis) and to hepatic injury including drug-induced liver injury (DILI) or increases in liver enzymes (aspartate transaminase [AST], alanine transaminase [ALT], alkaline phosphatase [ALK], gamma-glutamyl transferase [GGT] and bilirubin). The majority of patients presented with mild to moderate liver enzyme elevation, which was in most cases transient upon dose reduction or treatment discontinuation. However, severe DILI with fatal outcome has also been reported. Liver enzymes must be followed closely during treatment. Nintedanib must be dose-reduced, or interrupted in the event of hepatic toxicity and further treatment withheld until recovery of the abnormal laboratory parameters.

Based on data from clinical trials and post-marketing and supported by population pharmacokinetic models, patients with low body weight (<65 kg), Asian and female patients have a higher risk of liver enzyme elevations with nintedanib treatment.

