3.3.4.1 Discontinuation of trial treatment

An individual patient will discontinue trial treatment if:

- The patient wants to discontinue trial treatment, without the need to justify the decision.
- The patient experiences signs of hepatic injury, defined in Section [5.2.10.1.4](#).
- In the opinion of the investigator, the patient experiences unacceptable adverse events despite dose adjustments and supportive care.
- The patient has repeatedly shown to be non-compliant with important trial procedures and, in the opinion of both, the investigator and sponsor representative, is not willing or able to adhere to the trial requirements in the future.
- Pregnancy (refer to Section [5.2.10.2.4](#)).
- The patient needs to take concomitant medication that interferes with the investigational medicinal product or other trial treatment. See also Section [4.2.2](#) for restricted or not-allowed medication.
- The patient can no longer receive trial treatment for medical reasons (such as surgery, adverse events, or other diseases).

In case of a temporary reason, trial treatment should be restarted if medically justified, please see Section [4.1.4](#).

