4.1.4 Drug assignment and administration of doses for each patient

Patients will take one tablet of Microgynon[®] at least 3 days before the first intake of nintedanib (at Visit 2 in Period 1) and one tablet of Microgynon[®] after continuous nintedanib administration for at least 10 consecutive days (at Visit 6 in Period 2). The remaining 19 tablets in the Microgynon[®] blister will not be used.

Nintedanib will be taken by the patients at home except for the PK profiling days. The patients will be handed out the nintedanib medication (two bottles with 30 capsules each, containing 150 mg nintedanib per capsule, for the respective time period) at the time point indicated in the [Flow Chart](#).

Nintedanib will be administered orally on a twice daily basis (b.i.d.). The nintedanib capsule should be taken with food, swallowed whole with water (~250 mL) and must not be chewed or crushed. Nintedanib needs to be taken with a dose interval of approximately 12 hours, i.e. at approximately the same time every day: one capsule between 06:00 and 11:00 in the morning, and one capsule between 18:00 and 23:00 in the evening.

Nintedanib treatment (150 mg twice daily) will start at Visit 5 (Day 1) and will continue at stable dose for at least 14 days, in order to ensure that at least 10 days of continuous nintedanib treatment is taken before the PK profiling in Period 2 will start at Visit 6. The patient will have the last intake of nintedanib trial medication the evening prior to, or at the

End of Treatment (EOT) Visit, which has to take place at least 3 days after Microgynon[®] intake at Visit 6.

On both PK profile days (the first PK days in Period 1 and Period 2), a standardised meal (breakfast) has to be consumed within 30 minutes prior to Microgynon[®] intake. A standardized meal means that, for the individual patient, the meal should preferably be identical in Period 1 and Period 2. 30 Minutes after start of the standardised meal, Microgynon[®] will be administered. On the day of Microgynon[®] administration in Period 2, the morning dose of nintedanib will be taken first, immediately followed by the Microgynon[®] tablet and both have to be taken within one minute.

The trial drugs will be administered in the standing position under supervision of the investigating physician or an authorized designee.

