4.2.1.2 Management of liver enzyme elevation

Evaluate the concomitant use of other drugs known to cause liver enzyme elevations. For a detailed guidance on how to manage liver enzyme elevations, please refer to Table [4.2.1.2: 1](#).

Table 4.2.1.2: 1: Recommendations for managing liver enzyme elevations

	AST or ALT increase to			Hepatic injury ¹ (See also Section 5.2.10.1.4)
	>1.5x to <3x ULN	≥3x to <5x ULN and no signs of hepatic injury ¹	≥5x to <8x ULN, and no signs of hepatic injury ¹	
Period 1 (before nintedanib treatment)	Discontinue from study or justify continuation ²	Discontinue from study	Discontinue from study	Discontinue from study
Period 2 (on nintedanib treatment)	Continue as planned ^{2,3}	Reduce dose or interrupt nintedanib ^{4,5}	Interrupt nintedanib ⁵	Withdraw trial medication and discontinue study
		Close observation ⁶ After 2 weeks or any time later	Close observation ⁶ After 2 weeks or any time later	CLINICAL EVALUATION OF HEPATIC-INJURY (Section 5.2.10.1.4)
	<3x ULN	≥3x ULN	<3x ULN	≥3x ULN
	Reduced: Monitor bi-weekly for at least 8 weeks Interrupted: restart at reduced dose. Monitor bi-weekly for at least 8 weeks	Permanently discontinue trial Close observation ⁶	Restart at reduced dose Monitor weekly for 4 weeks, then bi-weekly for at least 8 weeks	Permanently discontinue trial medication. Close observation ⁶

Footnotes:

- ¹ A hepatic injury is defined by the following alterations of hepatic laboratory parameters (see Section 5.2.10.1.4:
 - a) ALT and/or AST ≥8 fold ULN
 - b) ALT and/or AST ≥3 fold ULN and total bilirubin ≥ 2 fold ULN*
 - c) ALT and/or AST ≥3 fold ULN and unexplained INR > 1,5*
 - d) ALT and/or AST ≥3 fold ULN and unexplained eosinophilia (>5%)*
 - e) ALT and/or AST ≥3 fold ULN and appearance of fatigue, nausea, vomiting, right upper abdominal quadrant pain or tenderness, fever and/or rash
 (Note * within the same blood sample)
- ² Investigator to confirm in writing that continuation is justified (e.g. intermittent fluctuation of transaminases).
- ³ According to visit schedule. Consider additional control visits as adequate.
- ⁴ To reduce or interrupt nintedanib is to be decided by Investigator and is based on individual risk assessment.

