5.2.10.1.4 Adverse events of special interest (AESI)

The term AESI relates to any specific AE that has been identified at the project level as being of particular concern for prospective safety monitoring and safety assessment within this trial, e.g. the potential for AEs based on knowledge from other compounds in the same class. AESI need to be reported to the sponsor’s Pharmacovigilance Department within the same timeframe that applies to SAE, please see above.

The following adverse events will be considered AESIs:

- Gastrointestinal perforation
- Hepatic injury

A hepatic injury is defined by the following alterations of hepatic laboratory parameters:

- h) ALT and/or AST ≥ 8 fold ULN
- i) ALT and/or AST ≥ 3 fold ULN and total bilirubin ≥ 2 fold ULN*
- j) ALT and/or AST ≥ 3 fold ULN and unexplained INR $> 1.5^*$
- k) ALT and/or AST ≥ 3 fold ULN and unexplained eosinophilia ($>5\%$)*
- l) ALT and/or AST ≥ 3 fold ULN and appearance of fatigue, nausea, vomiting, right upper abdominal quadrant pain or tenderness, fever and/or rash

* in the same blood draw sample.

These lab findings constitute a hepatic injury alert and the patients showing these lab abnormalities need to immediately stop the trial medication and need to be followed up according to the “drug-induced liver injury (DILI) checklist” provided in the ISF.

In case of clinical symptoms of hepatic injury (icterus, unexplained encephalopathy, unexplained coagulopathy, right upper quadrant abdominal pain, etc.) without lab results (ALT, AST and total bilirubin) available, the investigator should make sure these parameters are analysed, if necessary in an unscheduled blood test. Should the results meet the criteria of hepatic injury alert, the procedures described in the DILI checklist should be followed.

See also Table [4.2.1.2: 1](#) for recommendations on liver enzyme elevation during the trial and how to manage the trial medication and continuation of the trial.

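### For AST/ALT of 3x to <8x ULN at Visit 2, the note to the exclusion criteria permits continuation where the liver table calls for withdrawal

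*Protocol*

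**What the plan says.** Exclusion criterion 1 (Protocol Section 3.3.3) excludes patients with AST or ALT above 1.5x ULN. Criteria 2 and 3 do the same for bilirubin and creatinine clearance. One note covers all three. Visit 1 values must meet the limits. For later failure it says: "In case at Visit 2 the results do no longer satisfy the entry criteria, the Investigator has to decide whether it is justified" to keep her in the trial. The only condition is that the reason is documented.

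Section 4.2.1.2 has its own rule for transaminases. The first row of Table 4.2.1.2: 1, labelled "Period 1 (before nintedanib treatment"), has four bands. For >1.5x to <3x ULN the action is "Discontinue from study or justify continuation", with a footnote asking for written confirmation by the investigator. For the other three bands (3x to <5x, 5x to <8x, and hepatic injury) the only action is withdrawal from the study.

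Section 5.2.10.1.4 refers to this table for "recommendations on liver enzyme elevation during the trial and how to manage the trial medication and continuation of the trial". Section 3.3.4.1 requires trial treatment to stop if "The patient experiences signs of hepatic injury, defined in Section" 5.2.10.1.4. On dosing, Section 4.1.4 says: "Nintedanib treatment (150 mg twice daily) will start at Visit 5 (Day 1").

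**The concern.** The note and the table give different answers for the same blood sample. A patient eligible at Visit 1 who has ALT of 4x ULN at Visit 2, with no signs of hepatic injury, may stay under the note if the investigator writes a justification. Under the table she leaves the study.

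A patient who stays is scheduled to begin full-dose nintedanib at Visit 5. Section 1.2.1 reports drug-induced liver injury with fatal outcome on nintedanib and says that "Asian and female patients have a higher risk of liver enzyme elevations with nintedanib treatment". Every patient in this trial is a woman. Sites that read different pages would also treat the same result differently.

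**Working it through.** No sample-size or precision figure is involved. The check sets the two rules side by side over the AST/ALT range at Visit 2.

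**Do both rules apply to the same sample?** Yes. The detailed PK overview places Visits 2 to 4 in Period 1. The Flow Chart schedules safety laboratory tests at Visits 1, 2, 5, 6, EOT and FU, so Visit 2 is the only scheduled Period 1 sample. Section 6.2.1 ends screening at the first Microgynon intake, so the pre-dose Visit 2 sample could be called a screening sample. The overlap remains, because the table row is defined as before nintedanib and the note asks whether the patient stays in the trial, which is what the row decides.

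**Comparison by band**

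| AST/ALT at Visit 2 | Note, Section 3.3.3 | Table 4.2.1.2: 1, Period 1 row | Result |
|---|---|---|---|
| >1.5x to <3x ULN | investigator decides, documents | withdraw, or justify in writing | agree |
| 3x to <5x, no injury signs | investigator decides, documents | withdraw | conflict |
| 5x to <8x, no injury signs | investigator decides, documents | withdraw | conflict |
| hepatic injury | investigator decides, documents | withdraw | settled by 3.3.4.1 and 5.2.10.1.4 (treatment stops) |

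**Size of the gap**

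- Bands in conflict: 2 of 4.
- Lower edge relative to the entry limit: 3 / 1.5 = 2.0.
- Upper edge relative to the entry limit: 8 / 1.5 = 5.3.
- An eligible patient was at or below 1.5x at Visit 1, so to enter the conflict range her value must rise by a factor of at least 3 / 1.5 = 2.0 by Visit 2.

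**What happens if she stays and the value persists?** The Period 2 row at the same level says to reduce the dose or interrupt (3x to <5x), or to interrupt (5x to <8x). Neither row supports 150 mg b.i.d. at that level.

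**Would Visit 5 catch it?** Not dependably. Flow Chart footnote 7 says: "Laboratory safety test at Visit 5, Day 1 should be done prior to intake of nintedanib". Section 5.2.6 sends safety samples to a central laboratory, and nothing requires the Visit 5 result to be known before the first capsule. By contrast, the Flow Chart footnotes do require Visit 1 results to be awaited before Period 1.

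**Is such a rise plausible?** Stable methotrexate is permitted (Section 4.2.2.1) and bosentan is not restricted (Section 1.4.1). Section 4.2.2.2 names both as known to raise AST/ALT. The documents give no rate.

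**After the fix.** With the note limited to AST/ALT below 3x ULN, the two rules agree in all four bands.

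**The case against.** The two texts can be read together. The note is a general sentence over three laboratory criteria; it imposes a duty to decide and does not say that the patient may stay. The table is the specific rule for transaminases, and its first cell uses the same idea of justification and confines it to values below 3x. Withdrawing the patient satisfies both texts at every level. Section 5.2.6 also refers investigators to Section 4.2.1.2 for raised liver values, as do the opening of 4.2.1.2 itself and Section 5.2.10.1.4. Other safeguards exist: exclusion criterion 13 covers patients whom the investigator judges to be at risk, eligibility is reviewed again at Visit 2, and a value of 3x or more with symptoms such as nausea or fever already counts as hepatic injury. The statement about women concerns elevations on nintedanib, not values before it.

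Much of this stands. The sponsor very probably meant the table to govern, and few patients would be affected. But none of these references says that the table takes precedence over the note, and the table's title presents its content as recommendations. The mandatory stop in Section 3.3.4.1 covers hepatic injury only. A site could therefore keep the patient and point to protocol text that allows it.

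The Visit 5 pre-dose sample is drawn on the first day of Period 2, so it could be asked which row covers it. The row label, which refers to the time before nintedanib, largely answers that.

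**Conclusion.** The concern holds. For AST/ALT of 3x to <8x ULN without hepatic-injury signs at Visit 2, the note permits what the liver table rules out, and the protocol does not say which prevails. The conflict covers two of the four Period 1 bands. The number of patients cannot be derived from the documents and is expected to be small.

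The conclusion rests on reading Visit 2 as part of Period 1, as the Flow Chart does, and on the note having no unstated upper limit. It is a safety and consistency matter that should be corrected; the analysis model, the estimate and its precision are not affected.

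**What to change.** Add one sentence to the note in Section 3.3.3, for example:

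> For AST/ALT this discretion applies only below 3x ULN; a value of 3x ULN or more at Visit 2 is handled by the Period 1 row of Table 4.2.1.2: 1, and the patient is withdrawn from the study.

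Leave the discretion for bilirubin and creatinine clearance as it is. This uses the sponsor's own threshold and introduces no new one. An optional clarification is to state that the same row covers a Visit 5 pre-dose result known before the first capsule.

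The cost is one sentence and a letter to sites, with no added visits or tests. An occasional patient with a transient rise would be lost. The plan has room for this: about 24 enrolled for 14 evaluable leaves 24 - 14 = 10, and Section 7.7 allows further enrolment if fewer than 14 are evaluable.
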